12. ADVERSE EVENTS AND DEVICE DEFICIENCIES

12.1 DEFINITIONS

The categories of adverse events are shown in table 12.1-1. The definitions for each of these categories are given in the subsequent sections.

Table 3: Categories of Adverse Event

| | NOT DEVICE-RELATED | DEVICE- OR PROCEDURE-RELATED | |
|--------------------|-----------------------------|---|---|
| NON-SERIOUS | ADVERSE EVENT (AE) | ADVERSE DEVICE EFFECT (ADE) | |
| SERIOUS | SERIOUS ADVERSE EVENT (SAE) | SERIOUS ADVERSE DEVICE EFFECT (SADE) (SEE 12.1.3) | |
| | | ANTICIPATED | UNANTICIPATED |
| | | ANTICIPATED SERIOUS ADVERSE DEVICE EFFECT (ASADE) | UNANTICIPATED SERIOUS ADVERSE DEVICE EFFECT (USADE) |

CONFIDENTIAL AND PROPRIETARY

This document contains information that is confidential and proprietary to Smith & Nephew PLC and Smith & Nephew, Inc. and is intended for use only by Smith & Nephew and its manufacturer. It shall not be reproduced or copied in whole or in part, nor shall the contents be disclosed by any means without prior written permission from Smith & Nephew, nor shall anyone make any use of it that is contrary to the expressed or implied wishes of Smith & Nephew.

| | |
|--|---|
| Study Protocol—Device |  |
| A Prospective, Multi-center, Post-Market Clinical Follow-Up Study to Evaluate the Safety and Effectiveness of ALLEVYN Gentle Border | Number: ALLEV.PMCF.2017.13 |
| | Version: 3.0 |
| | Date: 21 JUN 2019 |
| | Page: Page 54 of 90 |

12.1.1 Adverse Event

An Adverse Event (AE) is any untoward medical occurrence between enrollment and treatment discontinuation associated with the use of an IP/Ancillary Product, whether or not considered causally related to that IP/Ancillary Product.

AE is used both to refer to AE which are non-serious non-IP or procedure-related and as an umbrella term referring to adverse events of all classifications.

An AE can be any unfavorable and unintended sign (for example, an abnormal laboratory finding), symptom, or disease. For reporting purposes, emphasis is placed first and foremost on whether or not the event constitutes an untoward medical occurrence.

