7.8 WITHDRAWAL

7.8.1 Withdrawal from Treatment

If a subject is withdrawn from study treatment the Treatment Discontinuation Case Report Form (CRF) needs to be filled out. However, the subjects will be followed up to the end of the study for safety assessments until day 28 (\pm 3 days).

Subjects may be withdrawn early from study treatment based on the decision of the investigator. This might include but is not limited to the following reasons:

- Closure of the reference wound
- Worsening condition of reference wound
- If the subject misses two (2) consecutive dressing changes/study visits, interrupting treatment for longer than seven (7) days
- A change in treatment that is clinically warranted
- An adverse event (AE)
- Concurrent illness
- Adverse device effects (ADE)
- Non-compliance (e.g. did not follow instructions)
- Lost to follow-up (LTFU)
- Any other significant reason identified by the Investigator

CONFIDENTIAL AND PROPRIETARY

This document contains information that is confidential and proprietary to Smith & Nephew PLC and Smith & Nephew, Inc. and is intended for use only by Smith & Nephew and its manufacturer. It shall not be reproduced or copied in whole or in part, nor shall the contents be disclosed by any means without prior written permission from Smith & Nephew, nor shall anyone make any use of it that is contrary to the expressed or implied wishes of Smith & Nephew.

| | |
|--|---|
| Study Protocol—Device |  |
| A Prospective, Multi-center, Post-Market Clinical Follow-Up Study to Evaluate the Safety and Effectiveness of ALLEVYN Gentle Border | Number: ALLEV.PMCF.2017.13 |
| | Version: 3.0 |
| | Date: 21 JUN 2019 |
| | Page: Page 32 of 90 |

Any subject that does not meet the minimum reference wound size requirement following wound size tracing at Visit 1 will be withdrawn. Subjects withdrawn from the study for this reason alone shall be replaced by enrolment of a new study subject. A new subject number will be assigned.

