8. STUDY DESIGN

8.1 STUDY DESIGN

This is a non-randomized, open label study in up to 8 study centres at maximum, conducted in up to 3 countries in Europe. The sample size is 40 subjects. There is no comparator group, however, subjects will be consecutively enrolled into 2 wound groups: A minimum of 10 subjects with acute wounds and a minimum of 10 subjects with chronic wounds.

Participation in the study will last 4 weeks (28±3 days) for each subject. All subjects will receive ALLEVYN Gentle Border as the study device, there is no control group. Subjects will be required to make at least one visit per week to the study center.

In total, 5 study visits are planned for each subject (day 0, day 7, day 14, day 21, day 28). The primary clinical endpoint (reduction of wound size) will be assessed at each study visit by using a specific camera. This camera will make a photograph of the wound in a standardized manner and will calculate the wound length, wound width and the depth of the wound automatically.

CONFIDENTIAL AND PROPRIETARY

This document contains information that is confidential and proprietary to Smith & Nephew PLC and Smith & Nephew, Inc. and is intended for use only by Smith & Nephew and its manufacturer. It shall not be reproduced or copied in whole or in part, nor shall the contents be disclosed by any means without prior written permission from Smith & Nephew, nor shall anyone make any use of it that is contrary to the expressed or implied wishes of Smith & Nephew.

| | |
|--|---|
| Study Protocol—Device |  |
| A Prospective, Multi-center, Post-Market Clinical Follow-Up Study to Evaluate the Safety and Effectiveness of ALLEVYN Gentle Border | Number: ALLEV.PMCF.2017.13 |
| | Version: 3.0 |
| | Date: 21 JUN 2019 |
| | Page: Page 33 of 90 |

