9. STUDY PROCEDURES

9.1 VISITS AND EXAMINATIONS

9.1.1 Summary

All subjects receive the ALLEVYN Gentle Border study device at visit 1 (Baseline, day 0). In total, all subjects need to perform 5 key study visits between week 1 and week 4, as shown in table 1. The visit schedule is based on the 7 days of maximum dressing wear time of ALLEVYN Gentle Border. The key visit date is counted from Baseline (day 0) and usually occurs on the same weekday in the following week. If a dressing change is required between the key visits the subject should come to an interim on-site visit (Routine Dressing Change Visit). A routine dressing change assessment will then be performed and documented in the Case Report Form. Then the subject

CONFIDENTIAL AND PROPRIETARY

This document contains information that is confidential and proprietary to Smith & Nephew PLC and Smith & Nephew, Inc. and is intended for use only by Smith & Nephew and its manufacturer. It shall not be reproduced or copied in whole or in part, nor shall the contents be disclosed by any means without prior written permission from Smith & Nephew, nor shall anyone make any use of it that is contrary to the expressed or implied wishes of Smith & Nephew.

| | |
|--|---|
| Study Protocol—Device |  |
| A Prospective, Multi-center, Post-Market Clinical Follow-Up Study to Evaluate the Safety and Effectiveness of ALLEVYN Gentle Border | Number: ALLEV.PMCF.2017.13 |
| | Version: 3.0 |
| | Date: 21 JUN 2019 |
| | Page: Page 35 of 90 |

continues with the next study key visit, counted from Baseline. If a subject is withdrawn from AGB treatment prior to key visit 5, this subject is still regarded as an active study participant. He/she should continue to come to the study key visit to follow-up with patients' safety up to visit 5.

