| 11. Record the total time that the subject spent at the visit (start to finish of wound care procedures). |
|---|

9.1.3 Study Visit 2 (day 7, ±3), Visit 3 (day 14, ±3), Visit 4 (day 21, ±3)

Visits 2 - 4 will be performed as on-site visits, so the subjects need to be present at each key study time point. These visits should take place every seventh (7) day. In case a dressing change is required before day 7, the instructions for a Routine Dressing Change Visit need to be followed (chapter 9.1.4).

Subjects who are already withdrawn from treatment and no longer require a dressing change shall be followed up on the study visits to collect safety information.

- | |
|---|
| 
 1. Question subjects regarding any changes in health or concomitant treatment. 2. Hand out the CWIS, Patient Assessment Scale and Pain Scale to the subject and allow sufficient time to complete it. 3. Photograph the dressing in situ prior to removal with the delivered digital camera. 4. Remove the old dressing and inspect the wound. Complete a wound assessment according to BWAT (see Section 9.2.4). 5. Assess the reason for dressing change, assess the ease of dressing removal and dressing leakage. 6. Record any debridement and the method of debridement, and take a photograph of the wound immediately prior to and following debridement. Note: Photographs are not necessary if the subject was withdrawn from treatment at a previous visit. 7. Redress the wound, if clinically indicated. 8. Record details of all dressings used (e.g. brand, size, etc.) as well as any treatment applied underneath the dressing. |
|---|

CONFIDENTIAL AND PROPRIETARY

This document contains information that is confidential and proprietary to Smith & Nephew PLC and Smith & Nephew, Inc. and is intended for use only by Smith & Nephew and its manufacturer. It shall not be reproduced or copied in whole or in part, nor shall the contents be disclosed by any means without prior written permission from Smith & Nephew, nor shall anyone make any use of it that is contrary to the expressed or implied wishes of Smith & Nephew.

| | |
|--|---|
| Study Protocol—Device |  |
| A Prospective, Multi-center, Post-Market Clinical Follow-Up Study to Evaluate the Safety and Effectiveness of ALLEVYN Gentle Border | Number: ALLEV.PMCF.2017.13 |
| | Version: 3.0 |
| | Date: 21 JUN 2019 |
| | Page: Page 37 of 90 |

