9. Assess the ease of applying the new dressing, including remains in place and repositioning (if applicable).
10. Instruct the subject to carefully follow the ulcer care instructions until the next dressing change and provide information concerning arrangements for future study visits.
11. Record the total time that the subject spent at the visit (start to finish of ulcer care procedures).
12. If any AE or DevD are observed or reported after application of study product, they must be reported as instructed in Section 12 (Adverse Events and Device Deficiencies).

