9.1.5 End of Study Visit (day 28, ±3)

The End of Study Visit will be performed as an on-site visit. This should coincide with the normal timing of dressing changes, i.e. seven (7) days.

1. Question subjects regarding any changes in health or concomitant treatment.
2. Hand out the CWIS, Patient Assessment Scale and Pain Scale to the subject and allow sufficient time to complete it.
3. Photograph the dressing in situ prior to removal with the delivered digital camera.
4. Remove the old dressing, inspect the wound and complete wound assessment according to BWAT (see Section 9.2.4).
Note: A full wound assessment is not necessary if the subject has already been withdrawn from treatment.
5. Assess the reason for dressing change, assess the ease of dressing removal and dressing leakage.
6. Record any debridement and the method of debridement, and **take a photograph of the wound immediately prior to and following debridement.**
7. Fill out the Study Completion CRF.

CONFIDENTIAL AND PROPRIETARY

This document contains information that is confidential and proprietary to Smith & Nephew PLC and Smith & Nephew, Inc. and is intended for use only by Smith & Nephew and its manufacturer. It shall not be reproduced or copied in whole or in part, nor shall the contents be disclosed by any means without prior written permission from Smith & Nephew, nor shall anyone make any use of it that is contrary to the expressed or implied wishes of Smith & Nephew.

| | |
|--|---|
| Study Protocol—Device |  |
| A Prospective, Multi-center, Post-Market Clinical Follow-Up Study to Evaluate the Safety and Effectiveness of ALLEVYN Gentle Border | Number: ALLEV.PMCF.2017.13 |
| | Version: 3.0 |
| | Date: 21 JUN 2019 |
| | Page: Page 39 of 90 |

- | |
|---|
| 
8. Record the total time that the subject spent at the visit (start to finish of wound care procedures).
 
9. If any AE or DD are observed or reported, they must be recorded as instructed in Safety Section 12.
 |
|---|

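### Section 12.1.1 ends the adverse event definition at treatment discontinuation, although subjects withdrawn from treatment stay in safety follow-up to day 28

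*Combined protocol and SAP*

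**What the plan says.** Section 12.1.1 sets both ends of the AE window: "any untoward medical occurrence between enrollment and treatment discontinuation associated with the use of an IP/Ancillary Product". The terms that follow depend on it. An ADE is an AE judged related to the product or procedure (12.1.2), an SAE or SADE is an AE or ADE that meets a seriousness criterion (12.1.3), and a USADE is a serious ADE (12.1.4).

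Other sections carry safety follow-up past the end of treatment:

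- Section 7.8.1, on subjects withdrawn from treatment: "the subjects will be followed up to the end of the study for safety assessments until day 28", with a ±3-day window.
- Section 9.1.1: "If a subject is withdrawn from AGB treatment prior to key visit 5, this subject is still regarded as an active study participant". The same paragraph asks such subjects to keep attending key visits, for safety, up to Visit 5.
- Section 9.1.3 (Visits 2 to 4): subjects already off treatment "shall be followed up on the study visits to collect safety information".
- Section 8.1: "Participation in the study will last 4 weeks (28±3 days) for each subject".
- Section 9.1.5, note to item 4, expects such subjects at the last visit: "A full wound assessment is not necessary if the subject has already been withdrawn from treatment".
- Table 1 gives treatment discontinuation its own column, marked as before end of study, and ticks the AE assessment at every key visit.

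**The concern.** The protocol schedules safety collection in a period in which, by its own definition, no new AE can arise. The definition governs two things: what a site must send to the sponsor within 24 hours (12.3), and what the safety summaries count (10.5). A site that follows 12.1.1 to the letter need not report an event that starts after the dressing is stopped. A site that follows the visit instructions would report it. The same event could then be counted at one site and not at another. The SAP may add safety summaries, but it cannot change what sites were required to report.

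The subjects concerned are those who stop treatment before day 28. Under 7.8.1 the reasons include a worsening wound, an AE or an ADE, where later events bear on device safety, and also wound closure. Section 5.2 makes safety data part of the secondary objective. Section 4.3.2 says there is no direct clinical evidence yet on the safety of the dressing with the new wound contact layer. The safety window should therefore be unambiguous.

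**Working it through.** The plan states no figure for this point, so the check is a comparison of passages followed by a subtraction of visit days.

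**Does another passage extend the onset window?**

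| Place | What it does | Extends onset past end of treatment? |
|---|---|---|
| 12.1.1, closing sentence | Stresses whether the event is an untoward medical occurrence | No; the time limit in the same section stands |
| 9.1.3 item 12 | AEs "observed or reported after application of study product, they must be reported as instructed in Section 12" | No; gives a start but no end, and refers back to Section 12 |
| 9.1.5 item 9 | "If any AE or DD are observed or reported, they must be recorded as instructed in Safety Section 12" | No; refers back to Section 12 |
| 12.3; 21.7 item 8a | Recording and reporting duties for AEs | No; both reuse the defined term |
| 12.5, 12.5.1 | Follow-up of events unresolved when the subject completes or leaves | No; covers ongoing events, not new onsets |
| 10.5 | AE summaries, including outcome and duration | No; sets no onset window |

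None of them resets the end point.

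**Are end of treatment and end of participation the same event?** Sections 7.8.1 and 9.1.1 and the Table 1 column heading keep them apart, because a subject can leave treatment and remain an active participant.

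**Length of the uncovered period for one subject.** Inputs are the nominal key visits in Table 1 (days 7, 14, 21 and 28) and the ±3-day visit windows. Days outside the definition = End of Study day − stop day. No stopping rate is assumed.

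| Stop visit | Nominal | End of Study visit at day 25 to 31, stop on nominal day | Both visits within ±3 days | Key visits left |
|---|---|---|---|---|
| Day 7 | 28 − 7 = 21 | 25 − 7 = 18 to 31 − 7 = 24 | 25 − 10 = 15 to 31 − 4 = 27 | 3 |
| Day 14 | 28 − 14 = 14 | 25 − 14 = 11 to 31 − 14 = 17 | 25 − 17 = 8 to 31 − 11 = 20 | 2 |
| Day 21 | 28 − 21 = 7 | 25 − 21 = 4 to 31 − 21 = 10 | 25 − 24 = 1 to 31 − 18 = 13 | 1 |

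Section 7.8.1 does not tie stopping to a key visit, so these rows are illustrations. Table 1 schedules an AE check at each key visit left.

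**The case against.** The best reply is that this is loose wording with a clear intent behind it. The safety visits after treatment would have little purpose if later events did not count, so a reasonable site will report them. The protocol also blurs the two end points elsewhere. Section 9.1.8 uses the Treatment Discontinuation CRF for subjects who leave the study early, Table 1 ticks the exit form in the treatment discontinuation column, and 7.8.1 lists loss to follow-up as a reason for withdrawal from treatment. On that reading the sentence in 12.1.1 simply means end of participation.

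Much of this stands. Loose wording is a likely cause, many sites will probably report, and different counting between sites is a possibility, not something shown. But it explains the conflict without removing it. Sections 7.8.1 and 9.1.1 separate the two end points explicitly, and every instruction to report leads back to the definition that contains the cut-off. It is also true that separate forms for end of treatment and for study completion already exist (7.8.1, and 9.1.5 item 7). What needs tidying is how 9.1.8 and Table 1 use them, and that is secondary to the definition.

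**Conclusion.** The concern holds. Section 12.1.1 contradicts Sections 7.8.1, 9.1.1 and 9.1.3 and Table 1, and nothing else in the protocol repairs it. For a subject who stops treatment at day 7, 14 or 21 and stays in follow-up, 21, 14 or 7 nominal days fall outside the AE definition. These are days of undefined status, not missed events. Subjects treated to day 28, and those who leave the study when treatment stops, are unaffected.

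No study-wide figure can be given, because the documents state no stopping rate, and zero affected subjects is possible. Sample size and power are not touched. The textual conflict is certain and its practical effect is uncertain. It should be fixed because the definition controls expedited reporting as well as the safety tables.

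**What to change.** - **12.1.1:** end the window at the end of the subject's study participation, meaning the End of Study visit at day 28 (±3), or earlier withdrawal of consent, withdrawal from the study or loss to follow-up. Add that the phrase on association with product use does not exclude events after the last dressing. Ending at withdrawal of consent agrees with 7.8.3, which bars further data collection from that point.
- **10.5:** add one sentence saying that AEs are summarised over that window.
- **9.1.8 and Table 1:** use one form for the end of treatment and another for the end of participation. This is a tidy-up.
- **12.5.1:** the rules for ongoing events can stay.

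The cost is a protocol amendment. Under Section 15 it needs approval by the protocol signatories, the ethics committee and, as applicable, regulatory authorities. That section also reserves amendments after study start for exceptional cases. Ten subjects had been enrolled under V2.0 by 19 June 2019 (Section 11), so the amendment should say how the window applies to subjects already enrolled or finished. No visit or assessment is added, because the AE checks to day 28 are already scheduled. Reported event counts may be slightly less favourable.

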12.1.2 Adverse Device Effect

An Adverse Device Effect (ADE) is an adverse event that, in the opinion of the investigator, is related to the IP or the procedure.

Not Related - An AE is considered to be not related to the use of an IP or the procedure when the effect is DEFINITELY UNRELATED or UNLIKELY to have any relationship to the use of the IP or the procedure;

Related – An AE is considered to be related to the use of an IP or the procedure when there is a POSSIBLE, PROBABLE, or DEFINITE relationship between the AE and the use of the IP or the procedure.

An ADE is further categorized depending on whether the criteria in section 12.1.3 and 12.1.4 are met.

CONFIDENTIAL AND PROPRIETARY

This document contains information that is confidential and proprietary to Smith & Nephew PLC and Smith & Nephew, Inc. and is intended for use only by Smith & Nephew and its manufacturer. It shall not be reproduced or copied in whole or in part, nor shall the contents be disclosed by any means without prior written permission from Smith & Nephew, nor shall anyone make any use of it that is contrary to the expressed or implied wishes of Smith & Nephew.

| | |
|--|---|
| Study Protocol—Device |  |
| A Prospective, Multi-center, Post-Market Clinical Follow-Up Study to Evaluate the Safety and Effectiveness of ALLEVYN Gentle Border | Number: ALLEV.PMCF.2017.13 |
| | Version: 3.0 |
| | Date: 21 JUN 2019 |
| | Page: Page 55 of 90 |

12.1.3 Serious Adverse Events and Serious Adverse Device Effects

An AE or ADE is considered a **Serious** Adverse Event (SAE) or **Serious** Adverse Device Effects (SADE) if, in the view of either the Investigator or the Sponsor, it:

- a) led to death,
- b) led to serious deterioration in the health of the subject, that either resulted in
 - 1) a life-threatening illness or injury, or
 - 2) a permanent impairment of a body structure or a body function, or
 - 3) in-patient or prolonged hospitalization, or
 - 4) medical or surgical intervention to prevent life-threatening illness or injury or permanent impairment to a body structure or a body function,
- c) led to foetal distress, foetal death or a congenital abnormality or birth defect

Note: Planned hospitalization for a pre-existing condition, or a procedure required by the study protocol, without serious deterioration in health, is not considered a serious adverse event.

12.1.4 Anticipated/Unanticipated Serious Adverse Device Effect

An Unanticipated Serious Adverse Device Effect (USADE) is a serious ADE which by its nature, incidence, severity or outcome has not been identified in the current version of the risk analysis report.

Note: An anticipated serious adverse device effect (ASADE) is an effect which by its nature, incidence, severity or outcome has been identified in the risk analysis report. Summary of risk analysis report and thus anticipated SADEs is communicated through the IFU and in protocol section 4.3.

12.1.5 Severity

The severity of every AE will be assessed by the PI or medically qualified site staff to whom the responsibility has been delegated and documented on the delegation of authority log. AE should

CONFIDENTIAL AND PROPRIETARY

This document contains information that is confidential and proprietary to Smith & Nephew PLC and Smith & Nephew, Inc. and is intended for use only by Smith & Nephew and its manufacturer. It shall not be reproduced or copied in whole or in part, nor shall the contents be disclosed by any means without prior written permission from Smith & Nephew, nor shall anyone make any use of it that is contrary to the expressed or implied wishes of Smith & Nephew.

| | |
|--|---|
| Study Protocol—Device |  |
| A Prospective, Multi-center, Post-Market Clinical Follow-Up Study to Evaluate the Safety and Effectiveness of ALLEVYN Gentle Border | Number: ALLEV.PMCF.2017.13 |
| | Version: 3.0 |
| | Date: 21 JUN 2019 |
| | Page: Page 56 of 90 |

be classified as mild, moderate, or severe, regardless of whether or not the AE are considered to be serious or non-serious. The classification should be based on the following definitions:

Mild - An event is mild if the subject is aware of, but can easily tolerate the sign or symptom;

Moderate - An event is moderate if the sign or symptom results in discomfort significant enough to cause interference with the subject's usual activities;

Severe - An event is severe if the sign or symptom is incapacitating and results in the subject's inability to work or engage in their usual activities.

